The group will continue to work with us for the duration of the project. We have budgeted for two further meetings over the duration of the project, and using guidance from the NIHR INVOLVE document 'budgeting for involvement', included £50 per person per meeting. To reduce burden, minimise risk relating to COVID-19 and maximise inclusivity of these meetings, members of the group can attend

virtually. Further advice will be sought into developing advertising, the participant information, the training provided for the physiotherapists, the communication of the project's progress (such as a newsletter) and on conclusions from any reports.

Predictors

The potential predictive factors will be self-reported using the secure website (www.managing-achilles-pain.com). These factors have been purposefully selected from prior research (6,8–10):

- Working Alliance measured by the Working Alliance Inventory Short-Form (WAI-SF) (11)
- Outcome expectation measured by the Global Rating of Change (12)
- Self-efficacy measured by the Pain Self-Efficacy Questionnaire (PSEQ) (13) .

Clinical outcomes

Changes in the self-reported measures of pain and disability will also be recorded using the website. Recent research has questioned the usefulness of the disease specific measure of disability, the Victorian Institute of Sports Assessment - Achilles (VISA-A) to accurately inform change in a patient's clinical status (14). Consequently, the primary clinical outcome measure will be the Lower Extremity Functional Score (LEFS) (15). The LEFS is recommended in current clinical guidelines to assess disability (5). Changes in self-reported pain will be measured the Numerical Pain Rating Scale (NPRS) (16).

Sample Size

With the significance level set at 5%, and adjusting for multiple testing, a sample size of 129 would provide more than 80% power to detect a minimum effect size of 0.3. Allowing for a 20% attrition rate, 159 participants will be recruited. The R project for statistical computing package (pwr.r.test) was used to calculate this sample size:

```
> pwr.r.test (r=.3,sig.level=0.05/6, power=.8,alternative="two.sided")
```

approximate correlation power calculation (arctanh transformation)

n = 128.9428

```
r = 0.3
sig.level = 0.008333333
power = 0.8
alternative = two.sided
```

Data Collection

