Data from the clinical outcome measures and predictive factors will be collected on three occasions; at baseline, six weeks later and finally at twelve weeks following completion of the baseline questionnaire. A participant's email and telephone number will be collected at baseline and used to invite them to take the follow up questionnaires. To maximise response rates, non-responders will be sent one email and one text message reminder at two weeks and four weeks after an anticipated response.

Data analysis

A multiple linear regression is fitted for the clinical outcomes difference (12 weeks minus baseline) of LEFS and NPRS. Independent variables of the multiple linear regression are the predictor variables WAI-SF, GRC and PSEQ. Three predictor variables and two clinical outcome measures result in six hypothesis tests which are adjusted for multiple testing by the Bonferroni method.

Backward selection as secondary analysis is applied to analyse if collinearities impact the influence of the three predictors. Possible centre effects are investigated by fitting an additive centre effect and interaction effects using an analysis of covariance model.

Dissemination

The findings from this research may influence decision making between a physiotherapist and a patient. As such, patients and physiotherapists will be the target audiences to reach.

Dissemination to patients and physiotherapists will take place once the study is complete. To ensure it is effective and wide-reaching, despite the potential of an ongoing pandemic, we will use the study website to host a blog and a summary

infographic (which will be made available to download) detailing the findings of the research. These will be written using Plain English guidelines ensuring it is accessible to patients. To supplement this, but with the aim of providing more 'research-rich' detail, an online lecture will be developed and will be through YouTube. The link to the website and YouTube channel will be emailed to all participants and physiotherapists taking part in the research, as well as promoted on social media platforms such as Twitter. These online strategies will incur no additional costs to the project.

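### The six-week LEFS and NPRS are collected but given no analytic role; using them would add a little precision and guard against dropout bias of either sign

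*Protocol*

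**What the plan says.** Under Data Collection, the protocol states that outcomes and predictors "will be collected on three occasions; at baseline, six weeks later and finally at twelve weeks following completion of the baseline questionnaire". Under Data analysis, the main model is fixed: "A multiple linear regression is fitted for the clinical outcomes difference (12 weeks minus baseline) of LEFS and NPRS". Its right-hand side is fixed too: "Independent variables of the multiple linear regression are the predictor variables WAI-SF, GRC and PSEQ".

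Two further analyses are named. One concerns the choice of predictors: "Backward selection as secondary analysis is applied to analyse if collinearities impact the influence of the three predictors". The other adds centre terms: "Possible centre effects are investigated by fitting an additive centre effect and interaction effects using an analysis of covariance model". Neither mentions a six-week outcome.

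Under Sample Size, "a sample size of 129 would provide more than 80% power to detect a minimum effect size of 0.3", and then: "Allowing for a 20% attrition rate, 159 participants will be recruited".

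The protocol does not describe the analysis as one of completers and gives no missing-data method. No SAP is at hand.

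**The concern.** A 12-week minus baseline difference does not exist for someone with no 12-week form. Unless something is imputed, the regression drops everyone lost by week 12, including those who reported LEFS and NPRS at six weeks. Those answers carry information about the missing 12-week values, and participants will have spent time giving them.

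Two things are at stake. The first is precision, in a study whose expected number of completers gives power very close to the 80% target. The second is bias: if how a patient is doing at six weeks affects whether the 12-week form comes back, completers may show a different predictor-outcome slope from the whole cohort. Predicting response is the purpose of the study, so that slope is the main result.

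**Working it through.** **Inputs from the protocol.** r = 0.3; two-sided alpha 0.05/6 = 0.00833; power 0.80; 129 analysable; 159 recruited; 20% attrition; outcomes at 0, 6 and 12 weeks.

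**Inputs assumed.**
- ρ, the correlation of 6- and 12-week change given the predictors: 0.3 to 0.8.
- f, the share of 12-week dropouts who gave six-week data: 0.25 to 1.
- The dropout mechanism, as listed in step 4.
- Predictors taken at baseline. Data analysis does not say which occasion supplies them.

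**1. The plan's own figure.** Correlation power by the arctanh transformation, as in the R function that the protocol cites, gives n = 128.94, hence 129. This agrees with the protocol.

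**2. Participants usable by the regression as written.** 159 × 0.8 = 127.2, so about 127 contribute and about 32 do not. Power is 79.2% at n = 127 (79.3% at 127.2) and 80.0% at 129.

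**3. Precision under random dropout.** With p2 = 0.8 (share with 12-week data) and p1 = 0.8 + 0.2f (share with six-week data, if all completers also answered at six weeks), the variance of the 12-week slope is proportional to

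V = ρ²/p1 + (1 − ρ²)/p2.

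The 12-week-only regression has V = 1/0.8 = 1.25. Effective n is 159/V, and the ratio of standard errors is √(V/1.25).

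- Least favourable, ρ = 0.3 and f = 0.25: V = 0.09/0.85 + 0.91/0.8 = 1.2434; effective n = 127.9; ratio 0.997.
- Most favourable, ρ = 0.8 and f = 1: V = 0.64/1 + 0.36/0.8 = 1.09; effective n = 145.9; ratio 0.934.

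| ρ | Effective n (f = 0.25 to 1) | Power | Reduction in SE |
|---|---|---|---|
| 0.3 | 127.9 to 129.5 | 79.6% to 80.2% | 0.3% to 0.9% |
| 0.5 | 129.1 to 133.9 | 80.1% to 81.8% | 0.7% to 2.5% |
| 0.7 | 131.0 to 141.0 | 80.8% to 84.2% | 1.5% to 5.0% |
| 0.8 | 132.2 to 145.9 | 81.2% to 85.7% | 1.9% to 6.6% |

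**4. Bias of the completers-only slope, by simulation.** Settings: N = 159, 20% dropout, one standardised predictor, ρ of 0.5 to 0.8, and a partial correlation of 0.3, so a true slope of 0.3/√(1 − 0.09) = 0.314.

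| Dropout depends on | Completers-only slope | Against 0.314 |
|---|---|---|
| Nothing, or the predictor only | about 0.314 | none |
| Poor six-week change, log-odds 1 per SD | about 0.29 to 0.31 | about 2-7% too small |
| The same, plus low predictor score, log-odds 0.5 per SD | about 0.25 to 0.28 | about 11-20% too small |
| The same, plus high predictor score instead | about 0.32 to 0.34 | up to about 8% too large |

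The second row moves by a percentage point or two with the six-week slope assumed. Separate runs with a true slope of 0.30 and log-odds 1.4 per SD gave biases of −0.0145 (ρ = 0.5) and −0.0229 (ρ = 0.7), that is 4.8% and 7.6%. In those same runs, letting the effect of early change on dropout itself vary with the predictor gave −0.07 to −0.09. I do not rest the point on that harsher mechanism.

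In the third row, power falls to roughly 54-67%. A likelihood estimator that also uses the six-week change returned about 0.31 to 0.32 in every row when all dropouts had six-week data. In the third scenario it returned 0.29 to 0.30 when only half did. With no six-week data from dropouts there is no repair.

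**The case against.** The strongest reply is that this is missing-data handling, which a protocol may leave to its SAP. Much of that stands. The protocol nowhere commits to a complete-case analysis. A reader might infer one from the difference score and the attrition allowance, but the text does not say it. Imputing 12-week outcomes and then fitting the stated regression would be compatible with the protocol, and a SAP could add it. What remains is narrower: the protocol fixes a single-time-point outcome, collects the same measures at six weeks, and gives them no use.

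It is also fair that regression on a change score at a fixed endpoint is a valid analysis, that attrition is allowed for, that reminders are planned, and that collecting an intermediate visit does not oblige the primary model to use it. The present plan is therefore not an error.

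Two stronger readings are tempting. The first is that dropout will pull the coefficients towards zero. The documents give no dropout mechanism; the bias is nil under some plausible patterns, modest under others, and away from zero if high scorers who do poorly early are the ones who leave. The second is that the lost data explain a serious power shortfall. They do not: 127 against 129 costs less than one percentage point and is a separate sample-size matter, and the upper power figures require every dropout to have answered at six weeks.

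**Conclusion.** The point holds as an inexpensive improvement. The six-week LEFS and NPRS have no stated role, and the regression fitted as written would set aside about 32 of 159 participants, whether or not they answered at six weeks.

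The precision gain is small, and under weak correlation or few six-week responders it is close to nothing. Protection against bias is the better reason to act. Its value depends on dropout being related to early response, and neither the size nor the direction of that bias can be settled from the protocol. The correlation, the share of dropouts with six-week data and the dropout mechanism are all assumptions here. The simulations also use one predictor rather than the three in the model, so the figures show orders of magnitude and are not forecasts.

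**What to change.** Keep the 12-week change as the target, with the three predictors and the six Bonferroni-adjusted tests as stated. Add a sentence or two choosing one of these:

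- impute missing 12-week LEFS and NPRS from the predictors and the baseline and six-week outcomes, then fit the stated regression; or
- fit a repeated-measures model to the change from baseline at 6 and 12 weeks, with visit, the predictors and predictor-by-visit terms, and test the 12-week slopes. Using change as the response keeps the same target as the stated regression.

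Report the completers-only regression as a sensitivity analysis. If a SAP already does this, a cross-reference in the protocol is enough.

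The cost is a missing-at-random assumption and slightly more analysis work. No new data, visits or participants are needed. Dropouts with no six-week form gain little from either method.

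### Which predictors survive backward selection does not show whether collinearity affects WAI-SF, GRC and PSEQ

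*Protocol*

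**What the plan says.** Under Data analysis, the primary model is defined as follows: "A multiple linear regression is fitted for the clinical outcomes difference (12 weeks minus baseline) of LEFS and NPRS". Its terms are then listed: "Independent variables of the multiple linear regression are the predictor variables WAI-SF, GRC and PSEQ". Three predictors and two outcomes "result in six hypothesis tests which are adjusted for multiple testing by the Bonferroni method".

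The next paragraph adds the analysis at issue: "Backward selection as secondary analysis is applied to analyse if collinearities impact the influence of the three predictors". This fixes both a method (backward selection) and the question it is meant to answer (collinearity). The protocol gives no removal criterion and does not say how the selection output is to be read as evidence on collinearity. It mentions no correlation matrix, no variance inflation factor (VIF), and no comparison of coefficients between models.

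**The concern.** Backward selection removes predictors according to how little they add to the fit. It does not measure how far they overlap. A removal has at least three possible explanations: no effect, too little power, or an effect shared with a correlated predictor. The surviving set does not separate them. Conversely, predictors that are both collinear and strongly predictive can all survive, and the selected model is then identical to the full one. Where correlated predictors are about equally predictive, the survivor is largely a matter of chance. Where one clearly dominates, selection usually finds it.

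What is at stake is interpretation. A measure dropped because it overlaps with another may be reported as not mattering. The Dissemination section expects the findings to bear on decisions made between physiotherapist and patient, and plans a blog and an infographic for patients.

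**Working it through.** **Inputs from the protocol.** Three predictors and two outcomes; planning effect r = 0.3; per-test level 0.05/6 = 0.00833, two-sided; 129 needed and 159 recruited with 20% attrition (Sample Size).

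**The plan's own figure.** The pwr.r.test algorithm gives n = 128.94, with power 0.8002 at 129. The Fisher z formula agrees: n = ((z₁₋α/₂ + z₀.₈)/atanh r)² + 3 = ((2.638 + 0.842)/0.3095)² + 3 ≈ 129.4. The stated 129 is reproduced, and this point does not contest it. The simulations use n = 159 × 0.8 = 127.2, taken as 127.

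**Assumptions, because the protocol gives no values.** Standardised normal predictors with equal mutual correlation ρ, normal errors, outcome variance 1. Removal at p>0.05 unless stated, with p>0.05/6 and AIC as alternatives. There were 3,000 to 5,000 data sets per setting; a repeat with a new seed agreed within simulation error.

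**Algebra.**
- VIF = (1+ρ)/((1−ρ)(1+2ρ)). At ρ = 0 it is 1. At ρ = 0.5 it is 1.5/(0.5 × 2) = 1.50, so standard errors grow by √1.5 = 1.22.
- Three equal joint coefficients b give a single-predictor coefficient of b(1+2ρ). At ρ = 0.5, b = 0.15 gives 0.30, b = 0.25 gives 0.50 and b = 0.30 gives 0.60.
- With one true predictor at 0.30 and ρ = 0.5, the other two have single coefficients 0.5 × 0.30 = 0.15 and joint coefficients 0.

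**Does the kept set respond to collinearity?**

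| Setting | Result | ρ = 0 | ρ = 0.5 |
|---|---|---|---|
| One true predictor, r = 0.3 | kept alone | 84% | 82% |
| Three joint coefficients of 0.30 | all kept | 91% | 92% |

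The same sets appear with and without collinearity. The second row is a strong-effect case (single-predictor r of 0.6 at ρ = 0.5). With single-predictor r = 0.5 at ρ = 0.5, all three are kept in about 47%.

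A wider check at n = 129 gives the same picture. With one true predictor, exactly one predictor is kept in 84% of runs at ρ = 0 and in 91% at ρ = 0.8, although VIF rises from 1.00 to 3.46. With no collinearity and three true coefficients of 0.2, at least one is dropped in 72% of runs, through limited power alone.

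**Which predictor survives?** Three equal predictors, single-predictor r = 0.3, ρ = 0.5:

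| Removal rule | Each is sole survivor | Exactly one kept | A given predictor is removed |
|---|---|---|---|
| p>0.05 | 20 to 22% | 63% | 53 to 56% |
| p>0.05/6 | 28 to 31% | 88% | 65 to 67% |
| AIC | 9 to 10% | 29% | 39 to 41% |

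At ρ = 0.3 the sole-survivor share is 7 to 8% each (p>0.05), so this part of the problem shrinks when correlation is low.

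**What does removal mean?** The share of removed predictors with p<0.05 in their own single-predictor model is 87% in the equal-predictor case at ρ = 0.5. With one true predictor it is 37% at ρ = 0.5 and 1.5% at ρ = 0. Mean single against joint coefficients of removed predictors are 0.25 against 0.08, 0.15 against 0.00, and 0.01 against 0.01 respectively. Being removed looks the same in all three cases; setting the two coefficients side by side tells them apart.

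**Do direct measures respond?** The 5th to 95th percentile range of the sample VIF is 1.00 to 1.05 at ρ = 0 and 1.30 to 1.83 at ρ = 0.5, with no overlap.

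**The case against.** The strongest reply is that the protocol never says the surviving set is the readout. Backward selection starts from the primary model and refits at each step, so the natural use is to compare full and reduced models, and that comparison does respond to collinearity. When one predictor survives, the ratio of full-model to reduced-model standard error has median 1.01 at ρ = 0 and 1.24 at ρ = 0.5, with 5th to 95th percentile ranges of about 0.99 to 1.03 and 1.14 to 1.36. With three joint coefficients of 0.15, selection turns a full model with nothing below 0.05/6 into a reduced model with something below it in about half of data sets at ρ = 0.5, against about 3% at ρ = 0. Further, the correlations are assumed, the case where all three stay needs effects well above the planning value (at r = 0.3 and ρ = 0.5 all three stay in about 0.4%), and the analysis is secondary.

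Much of this is right. The full-to-reduced contrast is informative for predictors that survive. Three things still stand. The protocol does not state that comparison. It yields no reduced-model coefficient for a removed predictor, which is where the question is most pressing. It yields nothing when all three stay. A survivor's reduced-model coefficient also estimates a different quantity from its joint coefficient and should not be read as independent influence. Nor is this just detail deferred to a statistical analysis plan: the protocol itself ties a named method to a purpose, and a later plan that keeps the sentence keeps the mismatch.

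**Conclusion.** The concern holds. The set of predictors kept by backward selection is not evidence for or against collinearity, and the protocol names nothing else for that purpose. That conclusion needs no particular correlation; the percentages do, and they are illustrations under assumed correlations, effects and removal rules. The practical risk is largest when the three measures are moderately correlated and similarly predictive, and small when correlation is low or one measure dominates.

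The consequence is confined to this secondary analysis. The six Bonferroni-adjusted tests come from the three-predictor model and the sample size does not depend on selection. It is worth correcting, but it does not threaten the main result.

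**What to change.** Replace the sentence on backward selection with wording such as:

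> As a secondary analysis we will report, for each outcome, the correlation matrix and variance inflation factors of WAI-SF, GRC and PSEQ, and each predictor's coefficient with 95% CI from its single-predictor model beside that from the three-predictor model, fitted to the same complete cases. Conclusions rest on the three-predictor model.

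Backward selection may stay if it is labelled exploratory. If it stays, the removal rule should be stated.

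These outputs exist for every predictor, whichever ones selection would keep. On average at ρ = 0.5, three equal predictors each move from 0.30 alone to 0.15 jointly, while a single true predictor stays at 0.30 and the other two move from 0.15 to 0. Individual data sets will vary around this (standard error about 0.085 alone and 0.10 jointly at n = 127).

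The cost is a wording change, 3 × 2 = 6 single-predictor regressions, and one correlation and VIF table per outcome, all on data already collected. The downside is that the added intervals are descriptive and not adjusted for multiplicity, which the report should say. The primary analysis and recruitment target do not change.
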